## 4.2 Study Design

This is a prospective, multicenter, blinding evaluation, non-inferiority, randomized controlled clinical investigation. A population of up to 440 eligible subjects with single de novo coronary lesions up to 36 mm in length, in vessels with  $\geq 2.25$  and  $\leq 4.0$  mm reference diameter stenosis will be randomized, 1:1, to receive either the BIOTRONIK Orsiro SES or the Abbott Xience Prime™ EES. Planned follow-up investigations include clinical evaluation at 1, 6, 12, 24, 36, 48 and 60 months post procedure. At the 9 months follow up visit all subjects will undergo angiographic evaluation.

## 4.3 Endpoints

### 4.3.1 Primary Endpoint

The primary endpoint is the in-stent late lumen loss at 9 months, as assessed by the core laboratory QCA analysis.

### 4.3.2 Secondary Endpoints

#### 4.3.2.1 Treatment Success Indicator

- 1) Device success, defined as attainment of  $\leq 30\%$  residual stenosis, TIMI=3, of the target lesion using the assigned study stent only.  
Note: Post-dilatation is allowed to achieve device success.
- 2) Lesion success, defined as attainment of  $\leq 30\%$  residual stenosis, TIMI=3, of the target lesion using any percutaneous method.
- 3) Procedure success, defined as attainment of  $\leq 30\%$  residual stenosis, TIMI=3, of the target lesion using the assigned study stent only without occurrence of in-hospital major adverse cardiac events (MACE; composite of all-cause death, Q-wave or non-Q-wave MI, and any clinically-driven TLR).

#### 4.3.2.2 Clinical Endpoints

The following endpoints were followed up at 1, 6, and 12 months post-procedure, and once annually for up to 5 years.

- 1) All-cause death
- 2) Cardiac death
- 3) Myocardial infarction
- 4) MI of the target vessel
- 5) Stent thrombosis
- 6) All serious adverse device effects (SADEs)
- 7) Target Lesion Revascularization, TLR
- 8) Target Vessel Revascularization, TVR
- 9) Target Lesion Failure (TLF), composite of cardiac death, target vessel Q-wave or non-Q wave Myocardial Infarction (MI), Coronary Artery Bypass Grafting (CABG), clinically driven TLR
- 10) Target vessel failure (TVF), composite of cardiac death, target vessel Q-wave or non-Q wave Myocardial Infarction (MI) and clinically driven TVR
- 11) Major adverse cardiac event (all-cause death, Q-wave, non-Q wave MI and clinically driven TLR)

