## 2.4 Previous Evidence of the Investigational DES

The Orsiro stent is investigational in China. However, the stent has received the CE Mark on February 23, 2011 and is currently approved for marketing in more than 55 countries worldwide with over 200,000 units distributed as of March 2014.

The development of the Orsiro stent system has been supported by an extensive clinical trial program designed to collect data on over 3,000 Orsiro-treated subjects in studies using the Xience Everolimus Eluting Stent System as a comparator. The Orsiro clinical trial program includes the BIOFLOW-I First In Man study; the BIOFLOW-II international randomized study against the Xience Prime™ stent with intravascular ultrasound (IVUS) and optical coherence tomography (OCT) subsets, the BIOFLOW-III international all-comers registry, the BIOFLOW-IV international randomized study against the Xience Prime™/Xpedition™ stent with a pharmacokinetic subset, and the BIOSCIENCE international, randomized all-comers study against the Xience Prime™ stent. Table 3-3 summarizes the key design elements of each Orsiro study. Currently, BIOFLOW I, BIOFLOW II, BIOFLOW III and BIOSCIENCE have been already completed.

**BIOFLOW-I** was a 30-subject feasibility study conducted at two sites in Romania. The purpose of the trial was to evaluate the safety and efficacy of the Orsiro stent in the treatment of single de novo lesions in native coronary arteries with a reference vessel diameter of 2.5 - 3.5 mm and lesion length of  $\leq 22$  mm. The primary efficacy endpoint was late lumen loss measured at 9 months post - index procedure. The primary endpoint of in-stent late lumen loss at 9 months was  $0.05 \pm 0.22$  mm, the safety indicator included composite of cardiac death, target vessel MI and clinically-driven TLR was 6.7% (2/30) at 1 year and 13.7% (4/30) at 2 years, and a composite rate of all-cause deaths, any MI and any revascularization of 16.7% (5/30) at 2 years.

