**BIOFLOW-II** was a prospective, multicenter, randomized (2:1), controlled, non-inferiority trial that enrolled 458 patients. The purpose of this trial was to compare the efficacy and safety of Orsiro SES with the Xience Prime™ Everolimus Eluting Stent (EES) in subjects with single de novo coronary artery lesions in up to two coronary arteries. Follow-up angiography demonstrated a mean in-stent late lumen loss of  $0.10 \pm 0.32$  mm for the Orsiro stent, compared to  $0.11 \pm 0.29$  mm for the Xience Prime™ stent. The non-inferiority hypothesis was confirmed. At 12 months, there were no significant differences between the two arms in MACE.

The **BIOFLOW-III** study was a prospective trial that enrolled a total of 1,356 subjects at 43 centers in 14 countries. The BIOFLOW-III registry enrolled an unselected subject population, including a high proportion of high-risk subjects presenting with diabetes (29.6%), small vessels (42.4%), acute MI (32.6%), and chronic total occlusions (4.3%). The primary endpoint is TLF rate at 12 months. The result was similar to BIOFLOW I and BIOFLOW II, with the rate of TLF at 5.1% at 12 months.

The **BIOSCIENCE** study was a prospective, multicenter, randomized, controlled trial that enrolled 2,119 subjects at 13 clinical sites in Switzerland. The purpose of this study was to directly compare the Orsiro stent with the Xience Prime™ stent in a large series of 'all-comer' subjects. At 12 months, the TLF rate for the Orsiro stent (6.5%) was non-inferior to the Xience stent (6.6%).

	BIOFLOW-I	BIOFLOW-II	BIOFLOW-III	BIOFLOW-IV	BIOSCIENCE
--	-----------	------------	-------------	------------	------------

Design	
 
Prospective
 
Multi-center
 
Non-randomized
 
Single-arm
 
	
 
Prospective
 
Multi-center
 
Randomized (2:1 vs Xience Prime)
 
	
 
Prospective
 
Multi-center
 
Non-randomized
 
Single-arm
 
Open label
 
	
 
Prospective
 
Multi-center
 
Randomized (2:1 vs Xience Prime/Xpedition)
 
	
 
Prospective
 
Multi-center
 
Randomized (1:1 vs Xience Prime)
 

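### Target lesion failure counts bypass surgery with no lesion, vessel or clinical-indication limit, so it is neither lesion-specific nor nested in target vessel failure

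*Combined protocol and SAP*

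**What the plan says.** Item 9 of section 4.3.2.2 builds TLF from cardiac death, infarction of the target vessel, and then "Coronary Artery Bypass Grafting (CABG), clinically driven TLR". CABG stands between commas as its own component. The target-vessel qualifier belongs to the infarction and the clinically-driven qualifier to TLR; neither is attached to CABG. The synopsis uses the same wording, so this is not a slip in one place.

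Item 10 reads: "Target vessel failure (TVF), composite of cardiac death, target vessel Q-wave or non-Q wave Myocardial Infarction (MI) and clinically driven TVR". It has no CABG component, and neither does MACE in item 11.

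Section 2.4 describes the safety measure of BIOFLOW-I as a "composite of cardiac death, target vessel MI and clinically-driven TLR", again without CABG. For BIOFLOW-III the same section gives only a result, "with the rate of TLF at 5.1% at 12 months", and for BIOSCIENCE 12-month TLF rates of 6.5% (Orsiro) and 6.6% (Xience). It does not list the components of TLF in either study.

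The documents supplied name TLR and TVR but do not define them.

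**The concern.** TLF is meant to capture failure at the stented lesion, and TVF failure anywhere in the stented vessel. A reader expects every TLF to be a TVF. An unrestricted CABG component breaks that order: surgery for disease in a vessel that never received a study stent makes the subject a target lesion failure.

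The missing clinically-driven qualifier matters in this design because section 5.7.3 brings all subjects back for angiography at 9 months. Bypass prompted only by what that scheduled angiogram shows, even in a non-target vessel, would count in 12-month TLF. The clinical events committee (section 11.5.1) adjudicates events, but this definition gives it no ground for setting such surgery aside.

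At stake are the meaning of the TLF rate, how it reads beside the TVF rate in the same report, and its comparison with a composite that omits CABG.

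**Working it through.** **The plan's own figure.** The only design calculation is for in-stent late lumen loss (section 8.1). Inputs are SD 0.41 mm, margin 0.41/3 = 0.137 mm, one-sided alpha 0.025, power 85% and 25% loss.

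- 2 × [(1.960 + 1.036) / (1/3)]² = 161.6. Adding the plan's term 1.960²/4 = 0.96 gives 162.6, or 161.8 with the margin rounded to 0.137.
- The plan's 162 per group is reproduced, and 162 / 0.75 = 216. TLF does not enter, so nothing here changes the sample size.

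**Which events count, as written.**

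| Event | TLF | TVF |
|---|---|---|
| Cardiac death | yes | yes |
| Infarction of the target vessel | yes | yes |
| Clinically driven TLR | yes | yes, if TLR counts as TVR |
| Clinically driven percutaneous TVR outside the target lesion | no | yes |
| Clinically driven CABG to the target vessel outside the lesion | yes | only if TVR includes surgery |
| CABG to a non-target vessel | yes | no |
| CABG that is not clinically driven, any vessel | yes | no |

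The last two rows are in TLF and not in TVF; the fourth row is the reverse. Neither endpoint contains the other. Cardiac death is not lesion-specific either, but it is in both composites and does not disturb the nesting.

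**Scale in year 1.** Inputs from the documents are 220 per arm (440 randomised 1:1) and 12-month TLF of 5.1% and 6.5% for Orsiro. The fraction c of subjects who become TLFs only through such CABG is an assumption, because the documents give no rate.

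- Base events per arm: 220 × 0.051 = 11.2; 220 × 0.065 = 14.3.
- Added at c = 0.5%: 220 × 0.005 = 1.1. Added at c = 1.0%: 220 × 0.010 = 2.2.
- Share of the resulting TLF events, c / (base + c): lowest 0.005 / 0.070 = 7.1%, highest 0.010 / 0.061 = 16.4%.
- With a wider range of c, 0.25% to 2%: 0.55 to 4.4 subjects per arm, and shares from 0.0025 / 0.0675 = 3.7% to 0.02 / 0.071 = 28.2%.

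These shares assume that the 5.1% and 6.5% exclude such surgery. If the earlier definitions already included it, adding it again would double count.

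**Effect on a difference between arms.** If such surgery strikes independently of arm and of other TLF events, a rate p becomes p + c(1 − p), and the risk difference is multiplied by (1 − c). At c = 0.5–1.0% it shrinks by only 0.5–1.0% of its size.

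**The case against.** The strongest reply is that this is a wording matter in one of eleven clinical secondary endpoints. Cardiac death, target-vessel infarction and TLR are also listed separately, so TLF could be recomputed without CABG and no new data. That stands, and it limits the harm. It does not settle which events the protocol-defined TLF counts.

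A second reply is that only target-lesion CABG was meant. That is plausible, but neither definition says so.

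Four stronger readings are tempting, and the documents do not support them:

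- **The CABG component is redundant and can be deleted.** A reader might infer that target-lesion bypass is already a TLR. TLR is never defined, so that is an assumption. Section 11.2.1 lists emergency bypass surgery, coronary rupture and vessel tears among the anticipated events of stenting. Emergency CABG for a complication at the stented lesion bears on the device or procedure, and deletion could drop it from TLF.
- **A non-inferiority conclusion is diluted.** TLF has no hypothesis, margin or power, and section 8.2.2 sets no non-inferiority test for it. The effect on a risk difference is negligible, as shown above. A ratio would move more visibly towards one, but no ratio analysis is planned.
- **TLF cannot be compared with any quoted earlier result.** The difference is shown only for the BIOFLOW-I composite. For BIOFLOW-III and BIOSCIENCE the components are not given, so comparability is unknown.
- **The TLF rate will exceed the TVF rate, or the excess will grow steadily to five years.** The first requires CABG-only failures to outnumber clinically driven TVR outside the target lesion, and the documents quantify neither. The second would extrapolate an assumed rate while ignoring attrition, death and subjects who have already failed.

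**Conclusion.** The definition is wrong as written in both places. It makes bypass surgery unrelated to the stented lesion, or not clinically driven, a target lesion failure without its being a target vessel failure. This conclusion follows from the text and needs no assumed rate.

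The consequence is limited to the interpretation of TLF, its relation to TVF, and its comparison with the BIOFLOW-I composite. The late lumen loss test, the 162 and 216 per group, and MACE, which the synopsis names as the main safety measure, are untouched. The year-1 scale of about 1–2 subjects per arm, or 7–16% of the resulting TLF events, rests on an assumed 0.5–1.0% and on the quoted rates excluding such surgery. Any charter or case report form that narrows the definition is outside the documents reviewed.

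**What to change.** In item 9 of section 4.3.2.2 and in the synopsis:

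1. Restrict the CABG component to clinically driven CABG of the target lesion, expressly including emergency CABG for a complication at the stented lesion. Do not simply delete it.
2. State that TLR and TVR each include percutaneous and surgical revascularization, and that TLR counts as TVR. For the nesting to hold, emergency CABG at the stented lesion must also be counted as clinically driven TVR. TLF then lies within TVF.
3. Report all CABG separately, whatever its target or indication, so that no surgery disappears from view.

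The cost is a short change of wording in two places, made before TLF is analysed. It needs no new visits, subjects or data and leaves the sample size alone. The downside is that the TLF rate may fall slightly.

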#### 4.3.2.3 Angiographic Endpoints

- 1) In-segment late lumen loss (LLL) at 9 months post-procedure
- 2) In-stent and in-segment (proximal and distal) minimum lumen diameter (MLD) at 9 months post-procedure
- 3) In-stent and in-segment binary restenosis rate angiographically assessed ( $\geq 50\%$  diameter

stenosis) at 9 months post procedure

4) In-stent and in-segment percent diameter stenosis (% DS) 9 months after procedure.

#### **4.4 Inclusion Criteria**

##### **4.4.1 Clinical Inclusion Criteria**

Subjects must meet all of the following criteria to participate in the trial:

- 1) Subject who can understand the investigation's goal has provided written informed consent, and is willing to comply with the study's follow-up requirements.
- 2) Subject is  $\geq 18$  years and  $\leq 75$  years old, male or female without pregnant.
- 3) Subject is an acceptable candidate for PCI.
- 4) Subject has clinical evidence of ischemic heart disease, stable or unstable angina pectoris or documented silent ischemia.
- 5) Subject is eligible for dual anti-platelet therapy treatment with aspirin, plus either, clopidogrel, prasugrel, ticagrelor or ticlopidine.

##### **4.4.2 Angiographic Inclusion Criteria**

Each target lesion/vessel must meet all of the following angiographic criteria for the subject to be eligible for the trial:

- 1) Target lesion must be in major coronary artery or branch (target vessel).
- 2) Target lesion must have angiographic evidence of  $\geq 70\%$  and  $< 100\%$  stenosis (by operator visual estimate).
- 3) Subject has up to two target lesions (two target lesions in one target vessel, or, for each target vessel, it has one target lesion).
- 4) Target lesion is suitable for drug-eluting stent PCI treatment.
- 5) Target lesion must be  $\leq 36$  mm in length by operator's visual estimate, and can be completely covered by one stent.
- 6) Target vessel must have a reference vessel diameter of 2.25–4.0 mm by operator's visual estimate.
- 7) Target vessel must have a Thrombolysis In Myocardial Infarction (TIMI) flow  $\geq 2$ .

#### **4.5 Exclusion Criteria**

##### **4.5.1 Clinical Exclusion Criteria**

Subjects will be excluded from the trial if any of the following criteria are met:

- 1) Subject is pregnant and/or breastfeeding or intends to become pregnant during the duration of the study.
- 2) Subject has clinical symptoms and/or ECG changes consistent with acute ST elevation MI (STEMI) within 7 days prior to the index procedure, hemodynamically unstable non-STEMI (NSTEMI) subjects included.
- 3) Subject is hemodynamically unstable.
- 4) Subject is an unacceptable candidate for CABG.
- 5) Subject has a known allergy to contrast medium that cannot be adequately premedicated, or any known allergy to thienopyridine, aspirin, both heparin and bivalirudin, L-605 cobalt-chromium (Co-Cr) alloy or one of its major elements(cobalt, chromium, tungsten and nickel), acrylic, fluoropolymers, silicon carbide, PLLA, sirolimus or everolimus.

- 6) Previous PCI of any target or non-target vessel 9 months prior to the index procedure.
- 7) Planned surgery within 6 months of the index procedure.
- 8) Planned staged treatment during the index procedure or within 30 days after the index procedure.
- 9) History of a stroke or transient ischemic attack (TIA) within 12 months prior to the index procedure.
- 10) Subjects with active bleeding disorders, active coagulopathy, or any other reason, who are ineligible for DAPT.
- 11) Subject will refuse blood transfusions.
- 12) Subject has documented left ventricular ejection fraction (LVEF)  $\leq 40\%$  as evaluated by angiography, echocardiogram, radionuclide ventriculography or any non-invasive imaging method within 90 days prior to the index procedure.
- 13) Subject is dialysis-dependent.
- 14) Subject has impaired renal function (i.e., creatinine  $> 2.0 \text{ mg/dL}$  or  $175 \text{ \mu mol/L}$  determined within 7 days prior to the index procedure).
- 15) Subject has leukopenia (i.e. WBC  $< 3.5 \times 10^9/\text{L}$ ), thrombocytopenia (plt $<100 \times 10^9/\text{L}$ ) or thrombocytosis (PLT $>350 \times 10^9/\text{L}$ ).
- 16) Subject is receiving chronic anticoagulation (e.g. coumadin, dabigatran, apixaban, rivaroxaban or any other agent).
- 17) Subject is receiving oral or intravenous immunosuppressive therapy (inhaled steroids are permitted), or has known life-limiting immunosuppressive or autoimmune disease (e.g., human immunodeficiency virus, systemic lupus erythematosus; diabetes mellitus is permitted).
- 18) Subject has life expectancy of  $< 3$  years.
- 19) In the investigator's opinion, subject will not be able to comply with the follow-up requirements.
- 20) Subject is participating in another (medical device or drug) clinical study. Subjects may be concurrently enrolled in a post-market study, as long as the post-market study device, drug or protocol does not interfere with the investigational treatment or protocol of this study.

#### 4.5.2 Angiographic Exclusion Criteria

Subjects will be excluded from the trial if any of the target lesions/vessels meet any of the following angiographic criteria:

- 1) Target lesion is located within a saphenous vein graft or arterial graft.
- 2) Target lesion has any of the following characteristics:
  - a) Lesion location is within the left main coronary artery, or within 3 mm of the origin of the left anterior descending (LAD) or left circumflex (LCX).
  - b) Involves a side branch of  $> 2.5 \text{ mm}$  in diameter.

*Note: Lesions within 3 mm of the origin of the right coronary artery may be treated.*

- 3) Target lesion is totally occluded (100% stenosis).
- 4) Target vessel has angiographic evidence of thrombus.
- 5) Target vessel/lesion is excessively tortuous/ angulated or is severely calcified, preventing complete inflation of an angioplasty balloon.
- 6) Target vessel was treated with brachytherapy any time prior to the index procedure.

### 5 ENROLMENT AND PROCEDURES

The enrolment, randomization and follow up process are outlined in Figure 2.

---

Figure 2 Clinical investigation flowchart

## 5.1 Informed Consent

If the basic screening of a subject's medical record meets the inclusion and no exclusion criteria, the subject should be given the clinical investigation informed consent information form and informed consent signature form (abbreviated as informed consent form). The informed consent form includes but is not limited to the following:

- Explanation of the clinical investigation
- Duration
- Expected benefits, risks or inconveniences
- Explanation of alternatives
- Medical record access and subject confidentiality
- Whether the data will be used for publications or submission for reimbursement support.

No clinical investigation specific examination may be performed before the subject has signed the informed consent signature form. Informed consent should be signed in accordance with the applicable regulations, the Declaration of Helsinki, Good Clinical Practice and ISO 14155:2011(E).

The person signing the informed consent shall:

- Avoid undue influence on subject's willingness to participate
- The subject's legal rights should be protected
- Make the subject understand the trial and provide ample time for the subject to consider his/her participation.
- Assure that the informed consent form is fully completed i.e. Including dated signatures of the subject or the subject's legal representative as well as the person obtaining the informed consent.

The signed informed consent form will be retained by the investigator and made available (for review only) to the clinical investigation monitors, auditors and inspectors on request. A copy of the signed and dated informed consent form must be provided to the subject.

## 5.2 Enrolment

Subjects are considered enrolled once they signed the informed consent signature form. However, the subjects are eligible for the clinical investigation only after fulfilling the in- and exclusion criteria. The Intention to Treat (ITT) and the CIP population will only be based on eligible subjects.

All target lesions must be treated in one procedure. Planned staged procedures are not allowed. Only Orsiro SES or Xience Prime™ EES may be implanted during the index procedure. There is no restriction in the enrolment of eligible subjects per site.

## 5.3 Baseline Examinations

Subject clinical investigation eligibility must be confirmed prior to the intervention, through the following tests and examinations:

- Demographics
- For premenopausal women, a pregnancy test must be performed within 72 hours prior to angiography
- Review of in- and exclusion criteria
- Physical examination and relevant medical history including anginal status or myocardial ischemia
- A 12-lead electrocardiogram within 72 hours of the intervention
- Laboratory examination with 7 days of the intervention, including:
  - Infectious diseases screening (hepatitis B surface antigen, hepatitis C antibody, syphilis

antibody (TPPA), and HIV antibody)

- Blood routine (total WBC count, platelet count, hemoglobin, hematocrit, and RBC count)
- Liver function test (ALT、AST)
- Serum creatinine
- Serum glucose
- Serum lipid (triglyceride, cholesterol, high density lipoprotein, low density lipoprotein)
- Cardiac biomarkers CK (optional), CK-MB and Troponin I and/or T

#### 5.4 Medication

Unless clinically contraindicated, all subjects should receive the medication regimen listed below (take each hospital and surgeon's general use into consideration). The use of GPIIb/IIIa inhibitors is allowed but not mandatory.

The generic name of all medications administered must be recorded in the subject's medical record.

